#### 6.2.1.1. Analysis of Compliance of SF-36 and EQ-5D

The number of questionnaires received will be tabulated by time point. Compliance with completion of SF-36 and EQ-5D questionnaires will be summarized for the questionnaires completed at each study visit (Day -7, Day 0, Day 7, Day 60 and day 67) and also for the questionnaires completed at home (Days 1 to 6 and Days 61 to 67). Compliance will be defined for each time point as follows:

$$\% \text{ Compliance} = 100 \times N1 / N2$$

Where:

N1 = number of subjects with a completed SF-36/EQ-5D questionnaire

N2 = number of subjects for whom a questionnaire is expected

# Statistical Analysis Plan

GlaxoSmithKline

Study alias & e-track number(s): ZOSTER-063 (204928)

Questionnaires are expected from all subjects who received at least one dose.

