5.5.2.11. Distribution and completion of SF-36 and EQ-5D questionnaires post-vaccination

The SF-36 PF component of the SF-36 questionnaire (only questions 3a through 3j, see [Table 15](#)) and EQ-5D daily questionnaires will be distributed to the subjects to take home following both vaccinations at Visit 2 and Visit 4. These questionnaires will need to be completed on a daily basis (Days 1 to 6) and must be returned at the next visits (Visit 3 and Visit 5). Additionally, during Visits 3 and 5, subjects will be asked to once again fill in the entire SF-36 and EQ-5D questionnaires on site. Completed questionnaires, collected at Visits 3 and Visit 5, will be transcribed into the eCRF (see Sections [10.6.2.3](#) and [10.6.2.4](#)).

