## 2. STUDY DESIGN

This study is a Phase III, open label, multi-center study with a single group.

DC = Diary Card.

† Visit 3 at Day 7 is defined as 7 days post dose 1 at Visit 2 (Month 0) and Visit 5 at Day 67 is defined as 7 days post dose 2 at Visit 4 (Month 2).

‡ Diary Cards distributed at Visit 2 and Visit 4 for solicited adverse events (Days 0–6) will be collected on Day 7 and Day 67 (Visit 3 and Visit 5), respectively.

§ Questionnaires distributed at Visit 2 and Visit 4 will be collected on Day 7 and Day 67 (Visit 3 and Visit 5), respectively.

\* The Month 3 contact will occur when the post-vaccination 2 (Days 0–29) diary cards have been received by site (returned by mail).

The following group names will be used for the statistical analyses:

Group order in tables	Group label in tables	Group definition for footnote
1	HZ/su	Herpes Zoster subunit vaccine

The following sub-groups will be used for the statistical analysis:

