### 6.2.1. SF-36 and EQ-5D

The SF-36 health survey and the EQ-5D questionnaires will be completed by all subjects at each study visits (i.e., Visit 1 Day -7, Visit 2 Month 0 (before the vaccination), Visit 3 Day 7, Visit 4 Month 2 (before the vaccination) and Visit 5 Day 67). Additionally, after each vaccination, the subjects will be given the questionnaires to take home and asked to complete only questions 3a through 3j of the SF-36 questionnaires and the entire EQ-5D questionnaires, on a daily basis on Days 1 to 6 post-vaccination.

Each of the 8 components of the SF-36 Questionnaire and the EQ-5D Utility and VAS scores will be presented at each scheduled visit (Day -7, Day 0, Day 7, Day 60 and Day 67) including the derived baseline values for each dose. In addition the SF-36 physical functioning score (PF) (based on questions 3a to 3j) and the EQ-5D utility and VAS scores will be presented on days 1 to 6 following each dose. Further details of the SF-36 components and EQ-5D Utility and VAS scores can be found in section [7.1.3](#).

The primary endpoint variable is the SF-36 Physical Functioning (PF) scale. The analysis will be performed on the subgroups detailed in [Table 1](#).

The 10 individual questions that form the SF-36 PF scale will be analysed on an individual basis. The three responses (Limited a lot, Limited a little, Not limited at all) to the individual questions will be assigned a score of 0, 50, or 100. In this way a baseline score and a mean score over the 7 days post each dose can be calculated for each individual question. Summary statistics of the change from baseline will be presented for each individual question.

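### Questionnaire compliance after dose 2 (Days 61 to 67) is divided by everyone who received at least one dose, so subjects never given dose 2 count as non-compliant

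*SAP*

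**What the plan says.** SAP 6.2.1.1 introduces its formula with "Compliance will be defined for each time point as follows" and defines the denominator as "N2 = number of subjects for whom a questionnaire is expected". It closes with the rule "Questionnaires are expected from all subjects who received at least one dose". Nothing in the section restricts that population for the time points after dose 2. The time points covered are the site visits (Days -7, 0, 7, 60 and 67) and the "the questionnaires completed at home (Days 1 to 6 and Days 61 to 67".

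Other sections tie the forms to the injection. SAP 6.2.1 says that "after each vaccination, the subjects will be given the questionnaires to take home". Protocol 5.5.2.11 says that the daily forms "will be distributed to the subjects to take home following both vaccinations at Visit 2 and Visit 4". The notes in SAP section 2 state that "Visit 5 at Day 67 is defined as 7 days post dose 2 at Visit 4 (Month 2".

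The documents foresee subjects who miss dose 2. Protocol 6.4 lists events that bar further doses but allows the subject to continue other study procedures. Protocol 9.2.2 separates withdrawal from the vaccine from withdrawal from the study. Protocol 9.2 says withdrawals are not replaced.

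For diary cards, SAP 7.2.2.7 uses a different denominator: the number of doses administered for the specified vaccination.

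**The concern.** After dose 1, every subject in the denominator has been vaccinated and given the forms, so the ratio measures form completion. On Days 61 to 67 the same denominator includes subjects who were given no forms and have no defined visit, so the ratio measures form completion and dose 2 receipt together.

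Change in SF-36 PF and in QALY after dose 2 are secondary endpoints, and a reader will use the compliance table to judge how complete those data are. A fall between doses could mean that vaccinated subjects stopped filling in forms, or that fewer subjects were vaccinated. The two have different implications, particularly if some subjects stopped because of reactions to dose 1, and the table cannot separate them. The dose 2 questionnaire rate would also rest on a different base from the dose 2 diary-card rate in the same report.

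**Working it through.** **Plan's own figures.** The documents state no expected compliance rate and no rate of missing dose 2. The only numerical base is Protocol 10.3, which reproduces: 1.96 × 21.2/√360 = 2.19 (stated as 2.2), and 360/0.90 = 400 enrolled. The 10% used there is a planning allowance for non-evaluable subjects, not a dose 2 dropout rate, so it does not supply d.

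**Inputs.**
- N = subjects with at least one dose (cancels from the rates; 400 for illustration).
- d = share of N never given dose 2. Not in the documents; assumed 2% to 15%.
- c = completion rate among dose 2 recipients at a given time point. Not in the documents; assumed 95%.
- Undosed subjects return no forms on Days 61 to 67. This follows from the distribution rule and the Day 67 definition, but is still an assumption.

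**Days 61 to 67.** The forms received are N1 = c × (1 − d) × N.
- SAP rule: 100 × N1/N = 100 × c(1 − d)
- Dose 2 denominator: 100 × N1/[(1 − d)N] = 100 × c
- Shortfall in percentage points: 100 × c × d

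| d | SAP rule, c = 95% | Dose 2 denominator | Shortfall (points) |
|---|---|---|---|
| 2% | 0.95 × 0.98 = 93.10% | 95% | 1.90 |
| 3% | 0.95 × 0.97 = 92.15% | 95% | 2.85 |
| 5% | 0.95 × 0.95 = 90.25% | 95% | 4.75 |
| 10% | 0.95 × 0.90 = 85.50% | 95% | 9.50 |
| 15% | 0.95 × 0.85 = 80.75% | 95% | 14.25 |

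The relative understatement is exactly d. In percentage points it is d × c, slightly less than d.

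**Why the reported rate cannot be interpreted alone.** With N = 400, a reported 85.5% is 342 forms. That is 95% of 360 dosed subjects (d = 10%), or 85.5% of 400 dosed subjects (d = 0).

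**Day 60.** This form is completed at Visit 4 before vaccination (SAP 6.2.1; Protocol 5.5.2.4), so it does not depend on receiving dose 2. Let q be the share of undosed subjects who still complete it. The SAP rule gives c(1 − d) + qd, and the shortfall against c is d(c − q). With d = 10% and c = 95%:
- q = 0: 0.10 × 0.95 = 9.5 points
- q = 50%: 0.10 × 0.45 = 4.5 points
- q = 95%: 0 points

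A dose 2 denominator would be wrong here. At d = 10% and q = 95%, 0.95 × 400 = 380 forms over 360 dosed subjects gives 105.6%.

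**Home window.** SAP 6.2.1 puts home completion on Days 1 to 6 after each dose, and the note in SAP 4.2 puts day 7 on site. For dose 2 that is Days 61 to 66 at home, with Day 67 at Visit 5. SAP 6.2.1.1 lists Day 67 under both.

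**The case against.** The best defence is that the closing sentence of SAP 6.2.1.1 was meant only to exclude enrolled subjects who were never vaccinated, leaving the definition of N2 to handle dose 2. That is possible, but the sentence is the only statement of who is expected, it follows a definition that applies to every time point, and it has no exception for dose 2. A programmer would follow it as written.

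Second, the dose-specific rate may be recoverable. SAP 6.2.1.1 tabulates questionnaires received by time point and SAP 7.2.2.7 tabulates doses injected. If the latter are shown by dose, a reader can divide one by the other. The printed figure is then best described as a completion rate over all vaccinated subjects under the wrong label. This limits the harm but does not justify the label.

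Three stronger inferences are tempting, and the documents do not support them:
- *That compliance is the plan's only check on missing quality-of-life data.* SAP 6.2.3 plans a sensitivity analysis limited to subjects with valid assessments on at least 4 of the 7 days after each dose. It is a per-subject rule that does not use N2.
- *That Day 60 is understated in the same way.* The full shortfall there is an upper bound, reached only if no undosed subject completes the form.
- *That an endpoint result is biased.* The table is descriptive. The primary endpoint follows dose 1, and Protocol 10.7 sets no success criterion.

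**Conclusion.** The point holds for Days 61 to 67. As written, N2 includes subjects who had no form to complete, and reported compliance is the recipients' rate multiplied by (1 − d). The direction is certain whenever d is above zero, provided undosed subjects return no forms and at least some dosed subjects do. The size is not known from the documents: across the assumed 2% to 15%, with 95% completion, it is 1.9 to 14.25 points. For Day 60 the documents support only a smaller, possibly zero, effect. The home-window slip is editorial. This is a minor defect in a descriptive table, worth correcting because it is cheap and because the SAP already uses a per-dose denominator for diary cards.

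**What to change.** Replace the closing sentence of SAP 6.2.1.1 with a denominator for each period:
- Time points up to Day 7: subjects who received at least one dose, as now.
- Day 60: subjects attending Visit 4, or subjects still in the study at that point. Choose one and state it. Do not use dose 2 recipients.
- Days 61 to 67: subjects who received dose 2.

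Report the number of subjects not given dose 2 beside the table. If a rate over all vaccinated subjects is also wanted, show it under a separate label such as completion rate. Change the dose 2 home window to Days 61 to 66, leaving Day 67 with the visits.

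The cost is a few words in the SAP and a changed denominator in one table. No new data are needed, because receipt of each dose is already recorded in the eCRF.

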## 6.2.1.2. Baseline Values

Baseline for dose 1 is defined as the mean of the assessments at day -7 and day 0. Dose 2 baseline is defined as the mean of the three assessments at day -7, day 0 and day 60 (day 0 for dose 2). See section [7](#) for further details.

## 6.2.2. EQ-5D Utility / Quality adjusted life years (QALY)

The calculation of the baseline and post baseline values for the analysis of QALY loss is detailed in section [7.1.3](#).

The 95% CI for Quality-adjusted life year (QALY) mean loss will be obtained using a multiple regression model on the change from baseline EQ-5D utility scores. The model will include age strata, gender and frailty status as the fixed effect.

The 95% CI for utility scores will be obtained pre- and post-vaccination separately assuming that utility scores were normally distributed with unknown variance.

## 6.2.3. Sensitivity Analysis

The complete list of adverse events observed in the study will be reviewed after database freeze and those events, not related to vaccination, which could significantly impact a subjects physical functioning, will be selected. An exploratory analysis of the primary endpoint will then be carried out excluding subjects who reported these events.

Additionally an analysis will be carried out to explore the sensitivity of the primary endpoint analysis and QALY loss to the completion of questionnaires. Only subjects with a valid assessment for at least 4 of the 7 days post each dose will be included.

# Statistical Analysis Plan

GlaxoSmithKline

Study alias & e-track number(s): ZOSTER-063 (204928)

## 6.3. Frailty Status

An assessment of frailty status will be done at Visit 1. Frailty status will be measured in relation to the accumulation of deficits using a frailty index (FI) calculated according to the model proposed by Mitnitski et al. [Mitnitski, 2001]. The different aspects of frailty composing the FI will be assessed through a series of certified tests and specific questions in the following domains:

- Cognition: a 30-point questionnaire that is used extensively in clinical and research settings to measure cognitive impairment called the Montreal Cognitive Assessment (MoCA);
- Physical status: criteria for the definition of frailty developed by Fried et al. [Fried, 2001] to categorize the physical frailty phenotype (PFP), the physical functioning category of the SF-36 questionnaire will be used as measure of the physical activity of the subject [Ryb, 2012];
- Depression and exhaustion: a screening test for depression and depressive disorder called the Center for Epidemiologic Studies Depression Scale – Revised (CESD-R);
- Multimorbidity: occurrence of a specific age dependent list of diseases based on the published work [Mitnitski, 2001]. The 14 medical history items are : High Blood Pressure, Heart Attack, CHF, Cerebrovascular disease, Cancer, Diabetes Mellitus, Arthritis, Chronic Lung Disease, Long Term Disability or Handicap, Stomach or Intestinal Ulcers, Migraine, Cataract, Hearing Problems and Glaucoma.
- Disability: assessment of the subjects' dependence on others to perform a list of specific daily activities (based on the published work [Mitnitski, 2001; **Error! Reference source not found.**, 2008]).

The range of the index is 0 to 36. The contribution of each component is as follows:

Category	Range
Medical History	0 – 14
Disability assessment	0 – 14
CESD-R depression scale	0 – 1
SF-36 PF score	0 – 1
Cognitive assessment (MoCA)	0 – 1
Unintentional weight loss	0 – 1
Weakness (grip strength)	0 – 1
Slow walking speed	0 – 1
Self-rating of health	0 – 1
Health change in last year	0 – 1
Total	0 – 36

# Statistical Analysis Plan

Study alias & e-track number(s): ZOSTER-063 (204928)

Each subject will be assigned to one of three categories, Non-Frail, Pre-Frail and Frail.

If the score is  $\leq 3$  then the subject is classified as Non-Frail. If the score is greater than 3 but less than or equal to 8 then the subject is classified as pre-frail. If the score is greater than 8 then the subject is classified as Frail.

A subject must have at least 30 non-missing components in order to be assigned a frailty index classification. However in the event that a subject with a partially completed frailty assessment has a score greater than 8 then the classification will be Frail even if the total number of completed responses is less than 30.

Further details of the Frailty index components can be found in [Appendix A](#)

## 6.4. Analysis of resource utilisation

An analysis of resource utilisation related to reactogenicity will be carried out. Resource use data to be collected include:

### 6.4.1. Medications

The specific medications taken in response to reactogenicity are detailed in the eCRF.

The percentage of subjects reporting such medication use during the solicited 7-day (Days 0-6) follow-up period after each dose will be tabulated overall and by age category. In addition a frequency table of each specific medication taken in response to reactogenicity will be presented by preferred term.

### 6.4.2. Medically Attended Visits

Details of reactogenicity-triggered medical attention (phone calls, visits to a general practitioner/emergency room, hospitalizations and specialists' visits) will be collected from day 0-6 post each dose and recorded in the eCRF.

The percentage of subjects reporting each medically attended visit during the solicited 7-day (Days 0-6) follow-up period after each dose will be tabulated by age category and dose (and overall) with exact 95% CI.

### 6.4.3. Missed time from work

Missed time from work can affect the subject and both dedicated and non-dedicated caregivers. The percentage of subjects with loss of working days will be tabulated. In addition summary statistics of the number of days lost per caregiver/subject will be presented.

## 6.5. Health Economic Cost Analysis

A full analysis of the costs associated with reactogenicity will be carried out at a future date. This analysis will be detailed in a separate SAP.

## 6.6. Analysis of safety

The primary analysis for safety will be based on the TVC. If the percentage of the vaccinated subjects excluded from the ATP cohort for safety is more than 5%, a second analysis based on the ATP cohort for safety will be performed.

Safety analyses will be performed by age stratum and frailty status (sub-groups are defined in [Table 1](#)).

When appropriate, tabulations will be presented overall and by time of occurrence relative to last vaccination (e.g., using windows such as Days 0 – 6, Days 0 – 29 and more than 30 days post-vaccination).

The following analyses will be performed for safety endpoints:

- The percentage of subjects with at least one local solicited AE, with at least one general solicited AE and with any solicited AE during the solicited 7-day follow-up period will be tabulated with exact 95% CI after each vaccine dose and overall. The same tabulation will be performed for grade 3; related and grade 3 related AEs;
- The percentage of subjects with at least one local AE (solicited and unsolicited), with at least one general adverse event (solicited and unsolicited) and with any AE during the solicited 7-day follow-up period will be tabulated with exact 95% CI after each vaccine dose and overall. The same tabulation will be performed for grade 3, related and grade 3 related AEs;
- The percentage of subjects reporting each individual general AE collected during the pre-vaccination period (Day -7 and Day 0 visits) will be tabulated with exact 95% CI.
- The percentage of subjects reporting each individual solicited local and general AE during the solicited 7-day-follow-up period will be tabulated with exact 95% CI. For all solicited symptoms, the same tabulation will be performed for grade 3 solicited AEs and for solicited general AEs with relationship to vaccination;
- Summary of temperature value by half degree increment reported during the 7-day (Days 0-6) post-vaccination period following each dose and overall doses and subjects. The same tabulation for fever with relationship to vaccination will be done;

# Statistical Analysis Plan

Study alias & e-track number(s): ZOSTER-063 (204928)

- Summary of temperature value by half degree increment taken reported during the 7-day (Days 0-6) post-vaccination period following each dose and overall doses and subjects **with no conversion rule**.
- Summary of temperature value by half degree increment **by route temperature** taken reported during the 7-day (Days 0-6) post-vaccination period following each dose and overall doses **with no conversion rule**.
- The number of days with each individual solicited local and general AE **during the solicited 7-day follow-up period** will be tabulated;
- The number of days with each solicited symptom local and general **during the whole post vaccination period** will be tabulated.
- The percentage of subjects with at least one local solicited AE, with at least one general solicited AE and with any solicited AE reported during the solicited 7-day follow-up period and **lasting beyond this period** will be tabulated with exact 95% CI after each vaccine dose and overall. The same tabulation will be performed for grade 3;
- The percentage of subjects with each individual solicited local and general symptoms **ongoing beyond the 7-day follow-up period** will be tabulated. The same tabulation will be performed for grade 3;
- The percentage of subjects with at least one report of unsolicited AE classified by the MedDRA Preferred Terms and reported up to 30 days after each vaccination will be tabulated with exact 95% CI. The same tabulation will be performed for grade 3 unsolicited AEs and for unsolicited AEs with a relationship to vaccination. The proportion of unsolicited AEs resulting in a medically attended visit (such as emergency room, out-patient visit, site investigator, etc.) will also be tabulated;
- Total number/percentages of doses followed by AEs will be tabulated;
- The percentage of subjects who started to use the medications within the 30-days post-vaccination will be tabulated.
- The percentage of subjects with at least one report of serious adverse event classified by the MedDRA Preferred Terms and reported during the whole post-vaccination follow up period will be tabulated with exact 95% CI;
- SAEs will be described in details;
- The proportion of subjects with at least one report of pIMDs classified by the MedDRA Preferred Terms and reported during the whole post-vaccination period (from dose 1 up to study end) will be tabulated with exact 95% CI.
- pIMDs will be described in detail.

## 7. STATISTICAL CALCULATIONS

### 7.1. Derived and transformed data

#### 7.1.1. Demography

##### Age at vaccination

Age will be calculated as the number of years between the date of birth and the date of first vaccination.

To ensure that the collection of date of birth will not jeopardise the privacy of Personally Identifiable Information (PII), only a partial date of birth (MMYYYY) will be collected.

Therefore, the 15th of the month will be used to replace the missing date.

In case the month is missing, the date will be replaced by the June 30th of the year.

Note that due to incomplete date, the derived age may be incorrect by 1 month when month is missing from the birthdate. This may lead to apparent inconsistency between the derived age and the eligibility criteria/the age category used for randomization.

##### Conversion of weight to kg :

The following conversion rule is used, the result is rounded to 2 decimals:

- Weight in Kilogram = weight in Pounds / 2.2
- Weight in Kilogram = weight in ounces / 35.2

**Conversion of height to cm :** The following conversion rule is used, the result is rounded to the unit (i.e. no decimal):

- Height in Centimetres = Height in Feet \* 30.48
- Height in Centimetres = Height in Inch \* 2.54

# Statistical Analysis Plan

Study alias & e-track number(s): ZOSTER-063 (204928)

